4.3. Measures Taken to Avoid Bias

The measurement of most toxicities using the CTCAE v4.0 and assessment of tumor size using the mRECIST v1.1 criteria represent objective endpoints.

4.4. Number of Subjects

Up to 36 subjects will be enrolled in the Phase 1 dose-escalation portion of the study, followed by approximately 140 to 192 subjects in the Phase 2 portion of the study.

4.5. Study Termination

The investigator retains the right to terminate study participation at any time, according to the terms specified in the study contract. The investigator is to notify the IRB or IEC in writing of the study's completion or early termination, and send a copy of the notification to the sponsor or sponsor's designee and retain 1 copy for the site study regulatory file.

The sponsor may terminate the study electively or if required by regulatory decision. If the study is terminated prematurely, the sponsor will notify the investigators, the IRBs and IECs, and regulatory bodies of the decision and reason for termination of the study.

5. TREATMENT OF SUBJECTS

5.1. Treatment Groups and Administration of Study Drug

Subjects in Phase 1 will receive doses according to cohort enrollment. Subjects in Phase 2 will receive the dose or doses selected by the sponsor upon review of Phase 1 data. Study treatment should begin as close as possible to the date of enrollment.

5.1.1. Epacadostat

All BID doses of epacadostat will be taken orally morning and evening, approximately 12 hours apart without regard to food. If the morning or evening dose is missed by more than 4 hours, that dose should be skipped and the next scheduled dose should be taken at the usual time. If the subject vomits, an additional dose should not be taken. Doses of epacadostat will be self-administered except the days scheduled to be given at the study clinic (see Section 7.6). Epacadostat should be taken just prior to beginning the infusion of durvalumab on days given in clinic. Epacadostat will be given daily in combination with durvalumab for up to 12 months. Intrasubject dose escalation of epacadostat is not permitted.

5.1.2. Durvalumab

The dose of durvalumab will be calculated based on the subject's weight in kilograms. Durvalumab will be administered in the clinic as an IV infusion of 3 mg/kg or 10 mg/kg once every 14 days for up to 12 months. Intrasubject dose escalation of durvalumab is not permitted except as defined in Section 5.6.1.

5.1.2.1. Durvalumab Treatment Administration

Durvalumab will be administered as an IV infusion over approximately 60 minutes (± 5 minutes). The IV line will be flushed with a volume of normal saline equal to the priming volume of the infusion set used after the contents of the IV bag are fully administered (unless prohibited by institutional practice). No incompatibilities have been observed between durvalumab and polypropylene, polyethylene, polyolefin copolymers, or polyvinylchloride.

Since the compatibility of durvalumab with other IV medications and solutions, other than normal saline (0.9% [w/v] sodium chloride for injection), is not known, the durvalumab solution should not be infused through an IV line in which other solutions or medications are being administered. The date, start time, interruption, and completion time of durvalumab administration must be recorded in the source documents.

5.1.2.2. Monitoring of Durvalumab Administration

Subjects will be monitored during and after infusion with assessment of vital signs at the beginning of the infusion (± 5 minutes), every 15 minutes (± 5 minutes) during the infusion of durvalumab, at the end of infusion (± 5 minutes), and at **30 minutes** (± 5 minutes) and **60 minutes** (± 5 minutes) postinfusion. Subjects will be monitored during a 3-hour (± 15 minutes) postinfusion period of observation after the first dose of durvalumab only. For subsequent doses, the 3-hour observation period will not be required unless a subject experiences

an infusion-related reaction. If the infusion takes longer than 60 minutes, then the vital signs assessments should follow the principles as described above.

In the event of \leq Grade 2 infusion-related reaction, the infusion rate of durvalumab may be decreased by 50% or interrupted until resolution of the event (up to 4 hours) and reinitiated at 50% of the initial rate until completion of the infusion. In subjects experiencing \leq Grade 2 infusion-related reaction, subsequent infusions may be administered at 50% of the initial rate. Acetaminophen and/or an antihistamine (eg, diphenhydramine) or equivalent medications per institutional standard may be administered at the discretion of the investigator. If the infusion-related reaction is \geq Grade 3 in severity, treatment with durvalumab will be discontinued. As with any antibody, allergic reactions to dose administration are possible. Appropriate drugs and medical equipment to treat acute anaphylactic reactions must be immediately available, and study personnel must be trained to recognize and treat anaphylaxis. The study site must have immediate access to emergency resuscitation teams and equipment in addition to the ability to admit subjects to an intensive care unit if necessary.

5.2. Treatment Compliance

Treatment compliance with all study-related medications should be emphasized to the subject by the site personnel, and appropriate steps should be taken to optimize compliance during the study. Subjects will bring all unopened, empty, and unused bottles of epacadostat with them to each study visit. Investigative site staff will perform a count of returned tablets to assess compliance, and this information will be entered into the CRF. Bottles of study drug, including unopened, partially opened, or empty bottles cannot be destroyed or returned to the depot until a monitor reviews and verifies all tablet counts for compliance. Compliance with durvalumab will also be documented in the medical record and monitored by the sponsor or its designee.

5.3. Randomization and Blinding

This is not a randomized or blinded study.

5.4. Duration of Treatment and Subject Participation

Each subject enrolled in the study will continue receiving combination study treatment in continuous 14-day cycles for up to 12 months as long as subjects are receiving clinical benefit and have not met any criteria for study withdrawal. When a subject discontinues all study treatment, the treatment period will end, the EOT visit should be conducted, and the subject will enter the safety follow-up period (see Section 6.4).

Protocol Amendment 6 (28 JUN 2017) removed the option for subjects to receive epacadostat monotherapy once they completed 12 months of combination therapy with durvalumab. However, subjects already receiving epacadostat monotherapy prior to Amendment 6 were allowed to continue if they were receiving clinical benefit and their investigator felt it was in the best interest of the subject. These subjects will be allowed to continue epacadostat monotherapy for up to an additional 12 months, and their maximum overall study treatment duration should not exceed 24 months. Exceptions for these subjects to continue study treatment beyond 24 months will require medical monitor review and approval every 3 months.

Study participation is expected to average about 6 months.

5.5. Rationale for Dose Modification

The purpose of the dose-escalation portion of the study (Phase 1) is to establish a suitable dose of epacadostat in combination with durvalumab.

A 42-day DLT window, along with regular internal reviews of safety events, will be used for the dose-escalation phase of the study. While the rules for adjudicating DLTs in the context of dose escalation/cohort expansion are specified in Section 5.5.1, an AE not listed above, or an AE meeting the DLT criteria above but occurring outside of the DLT period, may be defined as a DLT after consultation between the sponsor and investigator, based on the emerging safety profile. The final recommended dose for the dose-expansion phase will be based on the review of the safety and tolerability data, including cumulative toxicity from available cohorts.

Independent of the determination of tolerability during Phase 1 of the study, subjects may require individual modification or interruption of epacadostat or durvalumab if necessitated by AEs, including irAEs. Dose adjustments are summarized in Section 5.6.

5.5.1. Definition of Dose-Limiting Toxicities

Dose-limiting toxicities will be evaluated during the dose-escalation phase. The period for evaluating DLTs will be from the time of first administration of study treatment until the planned administration of the fourth dose of durvalumab, 42 days from receiving the first doses of epacadostat and durvalumab. Subjects who do not remain on the study up to this time for reasons other than DLT will be replaced with another subject at the same dose level. Grading of DLTs will be according to the NCI CTCAE v4.0. A DLT will be defined as the occurrence of any treatment-related toxicity described in Table 7 occurring up to and including Study Day 42 (6-week observation period). Only toxicities with a clear alternative explanation (eg, due to disease progression, comorbid conditions, concomitant medications) or transient (≤ 72 hours) abnormal laboratory values without associated clinically significant signs or symptoms based on investigator determination can be deemed non-DLT. Grade 3 irAEs (excluding ocular, pneumonitis, or colitis) that improve to \leq Grade 1 by appropriate care or corticosteroid therapy within 14 days after the initiation of supportive care or corticosteroid therapy will not count as DLTs. Subjects who may not have experienced a DLT but who experienced intolerable, lower grade persistent toxicity determined to be due to study drug or have experienced recurrent dose interruptions and/or reductions will be considered in the determination of the study drug doses to be used in Phase 2.

Table 7: Criteria for Defining Dose-Limiting Toxicities

Hematologic Toxicities:
 
• Grade 4 thrombocytopenia related to either drug• \geq Grade 3 neutropenia lasting $>$ 5 days related to either drug• Grade 4 anemia related to either drug• Febrile neutropenia ($ANC < 1.0 \times 10^9/L$ and fever $> 101^\circ F/38.3^\circ C$) related to either drug• Thrombotic thrombocytopenic purpura, hemolytic uremic syndrome, disseminated intravascular coagulation, idiopathic thrombocytopenic purpura, \geq Grade 3 hemolysis

Nonhematologic Toxicities:
 
• Any drug-related/immune-related^a Grade 4 toxicity• Any Grade 3 or 4 AST, ALT, or total bilirubin elevation• Any other drug-related/immune-related^a Grade 3 toxicity, EXCLUDING:
– Grade 3 nausea/vomiting controlled by medical intervention within 72 hours– Grade 3 immune-related AE^a (other than ocular events, colitis, and pneumonitis) that improves to Grade ≤ 1 or baseline within 14 days after the initiation of supportive care or corticosteroid therapy– Grade 3 endocrinopathy that is managed with or without systemic corticosteroid therapy and/or hormone replacement therapy and the subject is asymptomatic or minimally or transiently symptomatic based on Investigator assessment– Grade 3 fatigue lasting ≤ 7 days from onset– Grade 3 rash in the absence of desquamation, with no mucosal involvement, that does not require systemic steroids, that does not interfere with activities of daily living and resolves to Grade 1 by the next dose of durvalumab or 14 days, whichever is longer– Any grade vitiligo or alopecia• Grade 2 or higher episcleritis, uveitis, or iritis• Grade 2 pneumonitis that does not resolve to \leq Grade 1 within 3 days of initiation of maximal supportive care

General:
 
• Greater than 2-week delay in starting Cycle 4 because of a treatment-related toxicity even if the toxicity does not meet DLT criteria defined above.• If subjects are unable to receive 75% of epacadostat or 3 doses of durvalumab during the DLT observation period because of drug-related toxicity, even if the toxicity does not meet DLT criteria defined above.• While the rules for adjudicating DLTs in the context of dose escalation are specified above, an AE not listed above may be defined as a DLT after a consultation with the sponsor and investigators, based on the emerging safety profile.

^a Immune-related AEs are defined as AEs of an immune nature (ie, inflammatory) in the absence of a clear alternative etiology. In the absence of a clinically significant abnormality, repeat laboratory testing will be conducted to confirm significant laboratory findings prior to designation as a DLT.

5.5.2. Procedures for Cohort Review and Dose Escalation in Phase 1

Telephone conferences will be scheduled by the sponsor with Phase 1 investigators in order to review cohort-specific data, overall safety data from prior cohorts (if applicable), and to agree on dose escalation. For additional safety oversight, this group will review and adjudicate individual high-grade AEs as potentially dose-limiting and for guiding the study team on decisions regarding dose escalation and cohort expansion. The same method will be employed for reviewing data in Phase 1 to determine the recommended dose for Phase 2.

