1.3.2.2. Possible Risks Based on Clinical Data

As of 12 JUL 2015, > 1800 subjects have been treated across the ongoing durvalumab (MEDI4736) studies, including sponsored studies and collaborative studies. The majority of subjects have been treated with monotherapy durvalumab (n = 1279); however, 440 subjects have received MEDI4736 in combination with tremelimumab or other anticancer agents, 14 received other agents (1 gefitinib, 13 MEDI6383), and 150 subjects were blinded (mIB).

The safety profile of durvalumab as monotherapy and combined with other anticancer agents was consistent with the pharmacology of the target and other agents in the immune checkpoint inhibitor class. No tumor types appeared to be associated with unique AEs. Immune-related AEs, which are important risks of immune checkpoint inhibitors, have been observed with durvalumab and include colitis, pneumonitis, hepatitis/hepatotoxicity, neuropathy/neuromuscular toxicity, endocrinopathy, dermatitis, and nephritis.

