^a If event is a laboratory AE without associated clinically significant signs or symptoms, as determined by the principal investigator, the subject may continue study treatment administration with approval from the medical monitor as long as steroid treatment has not been planned or initiated. Laboratory testing should be repeated within 72 hours. If the AE does not resolve to \leq Grade 1 in 7 days, the subject should then interrupt study treatment until event has resolved to \leq Grade 1 and restart at the next lower dose level.

Table 9: Dose Reductions for Epacadostat

Current Dose	Dose Reduction
25 mg BID	Discontinue epacadostat
50 mg BID	25 mg BID
75 mg BID	50 mg BID
100 mg BID	75 mg BID
300 mg BID	100 mg BID

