5.6.3.3. Procedures and Guidance for Hepatitis

Monitor LFTs (hepatic transaminase, alkaline phosphatase, and bilirubin levels) and assess subjects for signs and symptoms of hepatotoxicity on Day 1 of each cycle before dosing of durvalumab. In subjects with hepatotoxicity, rule out infectious or malignant causes and increase frequency of LFT monitoring to twice per week until resolution. Recommendations for management of hepatitis are shown in [Table 12](#).

Table 12: Recommended Approach for Handling Hepatitis

Toxicity Grade	Withhold/Discontinue Epacadostat and Durvalumab	Guidance for Restarting Study Treatment	Supportive Care
Grade 1	No dose modifications. If it worsens, then treat as Grade 2 event.	Not applicable.	Increase frequency of LFT monitoring to twice per week until LFTs return to baseline.
Grade 2 elevation in AST/ALT or total bilirubin	Withhold epacadostat and durvalumab.	
Hold treatment until resolution to \leq Grade 1 or baseline.
 
 • If improves to \leq Grade 1 or baseline, resume study treatment after completion of steroid taper. Epacadostat will be reduced by 1 dose level, and durvalumab will resume at the same dose/schedule. • If toxicity worsens, then treat as Grade 3 or Grade 4. 	
 • Regular and frequent checking of liver chemistries (eg, every 1-2 days) until improving or resolved. • Rule out viral and other etiologies. • If event is persistent ($>$ 3-5 days) or worsens, promptly start prednisone 1-2 mg/kg per day PO or IV equivalent. • If still no improvement within 3-5 days despite prednisone 1-2 mg/kg per day PO or IV equivalent, consider additional work-up and start prompt treatment with IV methylprednisolone 2-4 mg/kg per day. • If still no improvement within 3-5 days despite 1-4 mg/kg per day methylprednisolone IV or equivalent, promptly start immunosuppressives (mycophenolate mofetil). Discuss with medical monitor if mycophenolate mofetil is not available. Infliximab should NOT be used. • Once improving, gradually taper steroids over \geq 28 days and consider prophylactic antibiotics, antifungals, and anti-PCP treatment (refer to current NCCN Guidelines for treatment of cancer-related infections [Category 2B recommendation]).

Table 12: Recommended Approach for Handling Hepatitis (Continued)

Toxicity Grade	Withhold/Discontinue Epacadostat and Durvalumab	Guidance for Restarting Study Treatment	Supportive Care

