Grade 3 elevation in AST/ALT of $> 5 \times \text{ULN}$ but $< 8 \times \text{ULN}$ OR Grade 3 elevation in total bilirubin of $\leq 5 \times \text{ULN}$	Withhold epacadostat and durvalumab.	Hold treatment until resolution to \leq Grade 1 or baseline. 
 • Resume study treatment if elevations downgrade \leq Grade 1 or baseline within 14 days; epacadostat will be reduced by 1 dose level, and durvalumab will resume at the same dose/schedule. • If AE does not resolve to \leq Grade 1 or baseline within 14 days: Discontinue study treatment (exceptions may be made by the medical monitor on a case by case basis). • Permanently discontinue study treatment for any case meeting Hy's law criteria (AST and/or ALT $> 3 \times \text{ULN}$ + bilirubin $> 2 \times \text{ULN}$ without initial findings of cholestasis (ie, elevated alkaline P04) and in the absence of any alternative cause. 	
 • Promptly initiate empiric IV methylprednisolone 1-4 mg/kg per day or equivalent • If still no improvement within 3-5 days despite IV methylprednisolone 1-4 mg/kg per day or equivalent, promptly start treatment with immunosuppressive therapy (mycophenolate mofetil). Discuss with medical monitor if mycophenolate is not available. Infliximab should NOT be used. • Hepatology consult, abdominal work-up, and imaging, as appropriate. • Once improving, gradually taper steroids over ≥ 28 days and consider prophylactic antibiotics, antifungals, and anti-PCP treatment (refer to current NCCN Guidelines for treatment of cancer-related infections [Category 2B recommendation]).
Elevation in AST/ALT of $> 8 \times \text{ULN}$ OR Elevation of total bilirubin of $> 5 \times \text{ULN}$	Discontinue epacadostat and durvalumab.	Not applicable.	

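### Section 5.5.1's text exempts recovering Grade 3 hepatic irAEs from DLT status, contradicting Table 7; Table 7 looks like the intended rule but no precedence is stated, and the effect is probably small or nil

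*Protocol*

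**What the plan says.** Protocol Section 5.5.1 handles DLT status in three moves. It defines a DLT by the treatment-related toxicities in Table 7, up to Study Day 42. It then says that only two kinds of event can be treated as non-DLT: those with a clear alternative explanation, and laboratory abnormalities of 72 hours or less without clinically significant signs or symptoms. The next sentence adds a third route: Grade 3 irAEs, except ocular events, pneumonitis and colitis, that recover to Grade 1 or less "within 14 days after the initiation of supportive care or corticosteroid therapy will not count as DLTs".

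Table 7 (Nonhematologic) lists "Any Grade 3 or 4 AST, ALT, or total bilirubin elevation" as a separate criterion with no recovery clause. Its own 14-day exclusion sits under the following criterion, which covers Grade 3 toxicities other than those already listed.

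Two General criteria in Table 7 also apply:
- "Greater than 2-week delay in starting Cycle 4 because of a treatment-related toxicity";
- subjects "unable to receive 75% of epacadostat or 3 doses of durvalumab during the DLT observation period because of drug-related toxicity".

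Hepatic events are irAEs in these documents. Protocol Section 1.3.2.2 says that immune-related AEs "have been observed with durvalumab and include colitis, pneumonitis, hepatitis/hepatotoxicity", Section 5.6.3.3 manages hepatitis as an irAE, and SAP Table 10 lists transaminase elevations among immune-related AEs.

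Neither Sections 5.5 to 5.5.2 nor the SAP says whether text or table prevails. Section 5.5.2 provides for case-by-case adjudication by the sponsor and Phase 1 investigators.

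**The concern.** Two written rules in one section give opposite answers for the same event, and the text is the less cautious of the two: it drops a liver event that the table counts. The DLT count feeds the 3 + 3 rule in Section 4.1.1, and Section 9.4.1 has the DLT rate summarized for each cohort. With cohorts of 3 or 6, the status of a single subject can matter to both.

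Liver toxicity is also a natural place to want a clean rule. Section 1.3.1 reports that epacadostat 300 mg BID with ipilimumab was stopped after Grade 3 or 4 ALT/AST elevation in 5 of 7 subjects. That was a different partner drug, so it explains the interest but says nothing about the rate with durvalumab.

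**Working it through.** **1. The two rules side by side.** Take an immune-related Grade 3 ALT elevation that lasts more than 72 hours and recovers to Grade 1 within 14 days of starting care.
- Section 5.5.1 irAE sentence: not ocular, pneumonitis or colitis; recovered in time; not a DLT.
- Table 7 hepatic criterion: a DLT, with no recovery clause.

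The recovery standards also differ: the text requires Grade 1 or less, while the table also accepts a return to baseline. The two wordings were not reconciled.

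**2. The plan's own figure.** Section 4.1.1 requires 75% of epacadostat doses, given as 63. Check: 42 days × 2 = 84 doses; 0.75 × 84 = 63. It reproduces.

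**3. Which events the dose-receipt criterion already catches.** After a Grade 3 hepatic event in the restart band of Table 12, epacadostat is held and then resumed one level lower, so cohort-level dosing ends at onset. Doses taken through Day d = 2d.
- Through Day 31: 62, one short of 63.
- The 63rd dose is the Day 32 morning dose.
- Before the Day 33 morning dose: 2 × 32 = 64.

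If the 75% means the cohort-specific dose, as in Section 4.1.1, an onset up to Day 31 is a DLT under either wording. From Day 33 the criterion is already met, and durvalumab doses 1 to 3 (Days 1, 15, 29) have been given.

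**4. Which events the Cycle 4 criterion catches.** Cycle 4 is due on Day 43, so a delay of more than 14 days means a start after Day 57. With care started on the day of onset, recovery within 14 days falls by onset + 14:
- Day 33 onset: Day 47.
- Day 42 onset: Day 56.

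Restart by Day 57 is therefore possible on the calendar for onsets on Days 33 to 42.

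**5. What restart requires.**
- Table 12's restart band is AST/ALT above 5 and below 8 × ULN, or Grade 3 bilirubin up to 5 × ULN. Higher values and Hy's law cases stop treatment; I take a permanent stop as falling outside the gap.
- The Grade 3 row allows restart on recovery "within 14 days; epacadostat will be reduced by 1 dose level, and durvalumab will resume at the same dose/schedule". It does not repeat the Grade 2 row's condition to "resume study treatment after completion of steroid taper".
- The same Grade 3 row calls for IV methylprednisolone 1 to 4 mg/kg per day and then a taper of at least 28 days. If restart waits for that taper, the earliest day is onset + 28: Day 61 for a Day 33 onset, Day 70 for a Day 42 onset. Both are after Day 57, so the event is a DLT under either wording.
- Section 5.6.2 requires discussion with the medical monitor before resuming after any interruption for liver test abnormalities.
- Section 5.6.3.12 allows restart after a withheld irAE once the taper is down to 10 mg/day prednisone equivalent. It covers irAEs not described elsewhere, so its reach to hepatitis is arguable. Illustration, with my assumptions (70 kg, 1 mg/kg, linear 28-day taper from the day of onset, no steroid conversion): 28 × (70 − 10)/70 = 24 days. A Day 33 onset reaches 10 mg on Day 57 and a Day 34 onset on Day 58. On that condition almost nothing escapes.

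**6. The other reading of the 75%.** If reduced doses count, 84 − 63 = 21 doses may be missed, and an earlier event with a hold of up to 10 days (84 − 20 = 64 doses) also has two statuses. This route is closed in Cohorts 1 and 2, where Table 9's step down from 25 mg BID is "Discontinue epacadostat".

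**The case against.** The strongest reply is that there is no real doubt about the rule. Section 5.5.1 defines DLTs by Table 7, then allows only two other kinds of event to be non-DLT. Table 7 gives liver tests their own criterion and attaches the 14-day exclusion to the remaining Grade 3 toxicities. The irAE sentence has the same three exceptions and the same 14 days as that exclusion, so it reads as a shortened restatement that lost its limit. This largely stands as evidence of intent. It does not remove the contradiction: the later sentence, followed as written, exempts the hepatic event, and no precedence is given. Adjudication under Section 5.5.2 decides individual cases; it does not say which written criterion applies.

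The second reply is that nothing turns on it. Phase 2 may use a PAD rather than an MTD (Section 4.2.1), the recommended dose rests on overall safety including cumulative toxicity (Section 5.5), and subjects with recurrent interruptions or reductions are considered even without a DLT (Section 5.5.1). Appendix E reports no DLTs in the first two cohorts (Amendment 3), few Grade 3 or higher transaminase elevations (Amendment 4), and neither hepatitis nor drug-induced liver injury in dose escalation (Amendment 5). This stands too. It bears on size, and few is not none.

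A reader might go the other way and infer a firm gap of 10 of the 42 observation days. The documents do not support that: calendar room to restart is not permission to restart, and the taper and medical-monitor conditions close most or all of it.

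**Conclusion.** The point holds as an internal inconsistency in a decision rule. The irAE sentence in Section 5.5.1 is wrong as written for immune-related hepatic events, because it contradicts Table 7, which the same section uses to define a DLT. Table 7 is very probably the intended rule.

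The affected group is narrow: an immune-related Grade 3 AST, ALT or bilirubin elevation lasting more than 72 hours, starting on about Days 33 to 42, within Table 12's restart band, recovering within 14 days, and restarting by Day 57 before the taper is complete and after discussion with the medical monitor. If sites wait for the full taper, the group is empty. This rests on reading the 75% as cohort-specific doses; if reduced doses count, the group is somewhat wider from Cohort 3 upward.

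A reader might infer that the selected dose is in doubt, since one reclassified subject can turn 0/3 into 1/3, 1/3 into 2/3, or 1/6 into 2/6, and each changes the 3 + 3 step. That is generic arithmetic for any one subject, not an expected effect here. The documents give no rate for these events, so no probability of a changed decision can be stated. Severity is low.

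**What to change.** Add AST, ALT or total bilirubin elevation to the exceptions in the Section 5.5.1 irAE sentence, or add a sentence that Table 7 prevails. Either is one line and takes the more cautious reading.

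Section 4.1.2 already has the expansion cohorts running at 300 mg BID, so the edit will not change an escalation step. The useful work is in the report: re-check Phase 1 Grade 3 hepatic events against Table 7, report the per-cohort DLT rates and the MTD or PAD on that basis, and flag in SAP Listing 16.2.7.3 any subject whose status would differ under the Section 5.5.1 text. If there are none, say so. Given what Appendix E reports, this is a check of very few events, with no new data collection.

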4.1.1. Phase 1 Dose Escalation

Phase 1 is the dose-escalation phase, which will include up to 6 cohorts of subjects treated with epacadostat at doses of 25 mg BID, 50 mg BID, 75 mg BID, 100 mg BID, and 300 mg BID in combination with durvalumab 3 mg/kg or 10 mg/kg given on Day 1 of each 14-day cycle. A minimum of 3 subjects will be enrolled and treated in each cohort, and all 3 subjects will be observed for a minimum of 42 days before the subsequent cohort begins enrollment.

Subjects must have received the cohort-specific dose of epacadostat for at least 75% of the doses (63 doses) and have received at least 3 doses of durvalumab during the 42-day DLT observation period, or have experienced a DLT to be evaluable for dose tolerability. Additional subjects will be enrolled in a cohort to achieve the minimum of 3 evaluable subjects if dropouts or dose interruptions/reductions occur that result in a subject being nonevaluable for DLTs.

The dose of epacadostat will be escalated if 0 of the first 3 evaluable subjects enrolled experience a DLT. If 1 of the first 3 evaluable subjects enrolled experience a DLT, the cohort will be expanded to include 3 additional evaluable subjects. If 2 or more of either 3 or 6 subjects enrolled experience a DLT, the prior dose level will be considered the MTD. If only 3 subjects were treated at this dose level, the dose will be confirmed as the MTD by evaluation of an additional 3 subjects before this dose is recommended for Phase 2 testing.

The cohorts and dose levels are shown in [Table 4](#).

Table 4: Dosing Cohorts

Cohort	Maximum Daily Dose of Epacadostat	Dose of Durvalumab (Once Every 14 Days)
1	25 mg BID orally	3 mg/kg IV
2	25 mg BID orally	10 mg/kg IV
3	50 mg BID orally	10 mg/kg IV
4	75 mg BID orally	10 mg/kg IV
5	100 mg BID orally	10 mg/kg IV
6	300 mg BID orally ^a	10 mg/kg IV

^a Intermediate dose levels may be explored based on emerging PK or pharmacodynamic data.

During the study, dose interruptions and/or dose decreases may be implemented based on toxicity as described in Section 5.6.

For the definition of DLT, see Section 5.5.1.

All subjects who received epacadostat and durvalumab in the dose-escalation phase and remain on study treatment will be observed for at least 42 days from the first dose prior to enrolling subjects in Phase 2 of the study.

4.1.2. Phase 2

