#### **4.1.2. Study Day**

The study day at a visit or reporting date will be calculated by the visit or reporting date minus the Day 1 date plus 1 (visit date - Day 1 date + 1). This study day will be subtracted by 1 if it is  $\leq 0$ , so that a study day of 0 will never occur. A study day of -1 indicates 1 day before Day 1.

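### The Table 7 criterion of a Cycle 4 delay over 2 weeks cannot be confirmed before about Study Day 58, yet the DLT window closes on Day 42 and the next cohort may open after 42 days

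*Protocol*

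**What the plan says.** - **The criterion.** The general items in Table 7 (protocol Section 5.5.1) include a "Greater than 2-week delay in starting Cycle 4 because of a treatment-related toxicity". It applies even if the toxicity would not otherwise be a DLT.
- **The window.** Section 5.5.1 runs the DLT period "until the planned administration of the fourth dose of durvalumab, 42 days from receiving the first doses of epacadostat and durvalumab". It then defines a DLT as "any treatment-related toxicity described in Table 7 occurring up to and including Study Day 42 (6-week observation period".
- **The escalation rule.** Under Section 4.1.1, durvalumab is "given on Day 1 of each 14-day cycle", and "all 3 subjects will be observed for a minimum of 42 days before the subsequent cohort begins enrollment". Escalation follows 0 DLTs in the first 3 evaluable subjects, and 1 in 3 leads to expansion to 6. A subject without a DLT is evaluable after at least 3 durvalumab doses and 75% of epacadostat doses (63) in the 42 days.
- **Late events.** Section 5.5 says that "an AE meeting the DLT criteria above but occurring outside of the DLT period, may be defined as a DLT after consultation" between sponsor and investigator.
- **Reporting.** Protocol Section 9.4.1 summarizes DLT rates by cohort, and the listings in SAP Appendix C include one of DLTs (16.2.7.3). The SAP does not restate the criteria or say how a delay still pending at Day 42 is classified.

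**The concern.** The criterion names an outcome that starts to accrue only when Cycle 4 is due, and the window ends at that same point. No rule says whether the cohort decision waits for a pending Cycle 4 delay, or what happens if the delay is confirmed after the next cohort has opened. In a 3 + 3 design one subject is decisive. If that subject is treated as DLT-free, new subjects can receive a higher dose before the event is countable. Two programmers building the DLT summary later could also classify the same subject differently, both with support in the text.

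**Working it through.** **Inputs.** Cycle length of 14 days, the 42-day minimum and the 63-dose threshold (protocol Section 4.1.1); DLT cut-off at Study Day 42 (Section 5.5.1); first dose on Day 1, with study day computed as "visit date - Day 1 date + 1" (SAP Section 4.1.2); visit window of ±3 days (protocol Table 24).

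**The plan's own figures reproduce.**
- Three cycles × 14 days = 42 days from first dose to the planned fourth durvalumab dose.
- 0.75 × 2 doses × 42 days = 63 epacadostat doses.

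**When the criterion is first met.**
- Planned Day 1 of Cycles 1 to 4: Days 1, 15, 29 and 43.
- Exactly 2 weeks late: 43 + 14 = Day 57. More than 2 weeks late: Day 58 or later.
- Gap to the cut-off: 58 − 42 = 16 days.

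| Reading of the schedule | Cycle 4 due | Criterion first met |
|---|---|---|
| As planned | Day 43 | Day 58 |
| Cycle 4 taken as due on Day 42 | Day 42 | Day 57 |
| One visit 3 days early | Day 40 | Day 55 |
| Three successive visits 3 days early | Day 34 | Day 49 |

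Every reading falls after Day 42.

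**Which subjects are exposed.** Suppose the lateness starts with a delay of 14 days at Cycle 3 and 14-day spacing is kept. Cycle 3 then falls on Day 43, so only 2 durvalumab doses are given by Day 42. A 14-day delay at Cycle 2 puts the doses on Days 1, 29 and 43, again 2 by Day 42. The neighbouring Table 7 item (fewer than 3 durvalumab doses, or under 75% of epacadostat, because of toxicity) already counts these subjects. What is left is a toxicity late in the window that holds Cycle 4 but leaves both dose thresholds met.

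**The protocol's own guidance can produce this case.** Take treatment-related Grade 2 enterocolitis starting on Day 33, before the morning dose. Table 11 recommends withholding both drugs, starting steroids promptly, tapering over at least 28 days once improving, and resuming after the taper.
- Durvalumab on Days 1, 15 and 29: 3 doses.
- Epacadostat through Day 32: 32 × 2 = 64 doses, above 63.
- Grade 2 enterocolitis meets no other specified Table 7 item.
- A 28-day taper starting no earlier than Day 33 runs to Day 60. The earliest restart is Day 61, and 61 − 43 = 18 days' delay, which is over 14.

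On Day 42 this subject is evaluable and DLT-free, and later meets the criterion.

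**Effect on decisions.** One such subject moves 0/3 (escalate) to 1/3 (expand), or 1/6 (within the MTD definition) to 2/6 (prior dose level becomes the MTD).

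**Illustration only; these rates are assumed.** P(escalate) = (1 − p)³ + 3p(1 − p)⁵. With a true DLT rate of 30% this is 49.4%. If 5 or 10 percentage points of that rate were Cycle 4 delays that all went uncounted, the apparent rates of 25% and 20% would give 60.0% and 70.9%. Table 32 implies 52.8% at 30% (100 − 47.2) rather than 49.4%; that difference is a separate matter.

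**The case against.** The strongest reply is that the Day 42 limit attaches to the toxicity, not to its consequences. A toxicity on Day 38 that later holds Cycle 4 for more than 2 weeks could then be a Table 7 DLT with late confirmation. Table 7 already has items that may be settled after Day 42, such as a Grade 3 immune-related event allowed 14 days to improve. This reading is tenable. It resolves how the subject is finally classified, but not the timing: the DLT is still unknown when the next cohort may open.

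Forty-two days is also a minimum. A subject who started at least 16 days before the last one reaches Day 58 when the last reaches Day 42. Sponsor and investigators must agree on escalation (Section 5.5.2) in roughly weekly calls (Section 8.7), so a held Cycle 4 would be visible. All this stands, but nothing requires waiting. Section 4.1.1 sets no stagger, and the last subject enrolled remains exposed. Section 5.5.2 speaks of adjudicating high-grade AEs, whereas the exposed cases can be lower grade. Section 5.5 is permissive and sets no deadline. Table 7's closing item likewise leaves unlisted AEs to consultation.

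A reader might infer that the criterion can never be met in time, or that the trial's DLT rates are understated. The documents support neither. Late review, earlier enrolment, the toxicity-based reading and the Section 5.5 clause each leave a route to counting the event, and the neighbouring dose-received item catches the longer Cycle 2 and Cycle 3 delays.

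Finally, Phase 2 cohorts at 300 mg BID were already enrolling by Amendment 6 (Section 4.1.2), so escalation appears to be over. That reduces the effect on future cohorts but not on the DLT summary.

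**Conclusion.** The point holds in a limited form. The Cycle 4 delay criterion is confirmed on about Day 58 at the earliest (Day 49 with every visit window stacked early), after both the Day 42 cut-off and the 42-day minimum before the next cohort. The gap affects a narrow group: a late-window toxicity that meets no other Table 7 item, with 3 durvalumab and at least 63 epacadostat doses received, in a subject not yet followed to about Day 58 when escalation is decided. For that group the outcome depends on discretion, although Table 7 presents the delay as a defining criterion.

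The size is one decisive subject per occurrence (0/3 to 1/3, or 1/6 to 2/6). No frequency is given, so no bias in the DLT rate can be claimed. The calendar result rests on 14-day cycles and first dose as Day 1. The enterocolitis example also assumes that Table 11's recommendation is followed without exception.

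**What to change.** The sponsor should reconcile Section 4.1.1, Section 5.5, the DLT definition in Section 5.5.1 and Table 7, so that the Cycle 4 criterion, the DLT window and the timing of the escalation decision agree. The text should say when a subject's status under this criterion is final, and whether the Day 42 limit refers to the toxicity or to the completed delay. The same rule should be written into the SAP and used for the per-cohort DLT summary and the DLT listing. Which clinical rule is right is for the sponsor to decide; the request is only that the sections give one answer.

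The cost is a short wording change in the protocol and one classification rule in the SAP. With escalation apparently complete, the remaining work is to check whether any Phase 1 subject had such a delay and to classify that subject under the stated rule.
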